Secondary outcome variables will include: completion of the iCBT program, number of telephone/email based coaching interactions, quality of life, measured using the EuroQOL-5D

(EQ-5D), healthcare utilization, measured using the Stanford Health Care Utilization Survey, and subject satisfaction with the program.

Background

Depression after stroke

Depression is common after stroke, occurring in up to one-third of all stroke patients.¹ A recent American Heart Association (AHA) scientific statement on post-stroke depression highlighted the importance of this condition, noting that it was “under-recognized, under-investigated, and under-treated.”² Individuals with depression after stroke have been shown to have lower functional status and lower quality of life than those without depression, irrespective of stroke severity, although the independent contribution of depression on outcomes is still not fully understood.

Traditional Cognitive Behavioral Therapy

Cognitive behavioral therapy (CBT) is an effective treatment for common mood disorders. Studies have shown a beneficial effect of CBT for both the treatment and prevention of depression after stroke.^{3,4} There is also evidence suggesting that CBT may provide a more durable and lasting treatment effect than pharmacotherapy with selective serotonin reuptake inhibitors.⁵

Despite the promise of CBT, its role in routine clinical practice is limited. There are significant barriers to widespread use of CBT. First, access to experienced CBT practitioners is limited.⁶ Second, the time and travel requirements to complete a course of CBT, which may require 2-3 visits per week for 10-12 weeks, are onerous for many patients. This may be even more difficult for patients with mobility limitations, which are common after stroke. Third, the cost of CBT may be prohibitive, particularly if providers do not accept insurance.⁶ Finally, patients may be resistant to in-person CBT because of stigma or fear of sharing deeply personal feelings with a therapist.

Technology and CBT

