- Patients without regular internet access through a computer, tablet or smartphone are excluded.
- Subjects requiring long-term inpatient nursing care are excluded. For patients enrolled as inpatients, individuals being discharged to both home and acute rehab are eligible. Individuals being discharged to a skilled nursing facility or hospice are excluded.
- Expected life expectancy less than 6 months or other inability to comply with study follow-up.
- Pregnant women and prisoners are excluded

Vulnerable populations: Children, pregnant women, fetuses, neonates, and prisoners are not included in this research study.

Sample Size: 20 subjects will be enrolled.

Accrual: The comprehensive stroke center at the Hospital of the University of Pennsylvania (HUP) is a tertiary referral center for acute ischemic stroke, with annual case volumes of approximately 600 strokes per year on the inpatient stroke service. Additionally, the stroke team sees patients in the outpatient clinic both in follow-up from their acute hospitalization and in consultation to provide second opinions for patients treated elsewhere. Due to the broad inclusion criteria of this study, it is expected that many of the patients seen, both inpatient and outpatient, will be eligible for participation in this study. We expect that we will be able to enroll 1-2 patients per week and will complete enrollment within 6 months.

Recruitment: A stroke physician evaluates all patients with acute ischemic stroke who present to HUP. All stroke team physicians will be trained investigators in this study, and they will screen patients for eligibility during routine clinical care. Study physicians will also screen for potentially eligible subjects during outpatient clinic sessions. All eligible subjects will be informed of the study, and if they are interested in participation, a study physician will obtain informed consent. The original signed consent form will be kept in the study binder. A copy of

the signed consent form will be given to the patient and another copy will be placed in the medical record.

Procedures

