Joyable is a commercially available 8-week program that consists of 5-6 online activities per week, for a total of 42 activities. Most activities can be completed within approximately 5-10 minutes. Activities cover the core elements of CBT: psychoeducation, cognitive restructuring, and behavioral activation. In addition to the digital program, as a part of the Joyable product, all participants will be assigned a coach. The role of the coach is to provide accountability, motivation, emotional support, and guidance, leading clients to get the most out of the iCBT program. They provide this support through a combination of phone, text, and email interactions determined by the client. Joyable coaching is defined by 3 pillars: Motivational Interviewing (MI), Program Knowledge, and Client Experience. All coaches are trained to competency in MI, an evidence-based method for structuring conversations to harness a person's intrinsic motivation to change. MI has been shown to increase engagement and improve client outcomes. Coaches attend a rigorous 1-month training course, biweekly booster sessions, and submit tapes of client communications until they reach competency. In addition to MI, coaches are trained in the iCBT program and how to support clients with obstacles that may arise and effectively deliver program knowledge to drive client success. At the time of study enrollment, we will assist the subject in scheduling their first contact with their assigned coach.

72 Hour Telephone Encounter

Subjects will be contacted by the study team in person or by telephone 72+/- 24 hours after enrollment to troubleshoot any technical difficulties accessing the Joyable program.

30 Day Telephone Encounter

Subjects will be contacted by the study team phone or in person at 30 days +/- 7 days after enrollment to assess technical difficulties using the Joyable program, functional status using the modified Rankin scale, and quality of life using the Euroqol EQ-5D.

90 Day In-person Visit

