Subjects will be seen by the study team 90 days +/- 14 days after enrollment to assess their neurologic function using the NIHSS, mood using the PHQ-9, functional status using the modified Rankin Scale, Quality of life using the Euroqol EQ-5D,^{20, 21} healthcare utilization using the Stanford Health Utilization survey,²² whether any other treatment for mental health problems was received (including medication and psychotherapy) and perceived utility of Joyable iCBT for depression as well as perceived barriers to successful use of internet-based CBT.

Table 1. Study measures and timing of assessment

	Baseline	72 hr Call	30 day call	90 day visit
Demographics	X			
Stroke information	X			
SSRI Use	X		X	X
Assess for technical problems		X	X	
NIHSS	X			X
mRS	X		X	X
EQ-5D	X		X	X
SHU				X
PHQ-9	X			X
Semi-Quantitative assessment of perceptions about Internet-based CBT				X

NIHSS=National Institute of Health Stroke Scale, EQ-5D=Euro-Qol 5D, SHU=Stanford Health Utilization survey, PHQ-9=Patient Health Questionnaire 9,

Analysis Plan

The baseline demographic variables of the study population will be summarized using means, medians, and proportions as appropriate. For each subject, we will calculate the total amount of time spent interacting with the Joyable program and the total number of Joyable activities that the patient successfully completed. We will then calculate averages across the study population. These metrics will provide important information on the average “dose” of CBT received. In an exploratory analysis we will look for relationships between baseline clinical and demographic factors and number of activities completed.

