We will calculate the average PHQ-9 score at enrollment and 90 days. We will compare the PHQ-9 score from enrollment to day 90. The statistical power of this test is uncertain. In Table 2 we present estimated study power (with $\alpha=0.05$) across a range of assumptions about both the change in PHQ-9 over time and the standard deviation of the difference in PHQ-9 over time. These calculations show that although this is a small pilot study, we have >80% power to detect a difference in PHQ-9 of 3 or more points across a range of assumptions. The PHQ-9 will also be administered to subjects weekly via through the Joyable program. We will examine whether there are significant changes in score over time using repeated measures analysis (generalized estimating equations, GEE) with PHQ-9 score as the dependent variable and week as the independent variable.

In an exploratory analysis, we will divide patients into two groups based on PHQ-9 at study completion (*high depression symptoms*, defined as median or above and *low depression*

symptoms, defined as below the median score). Healthcare outcomes, including modified Rankin scale, health related quality of life, and healthcare utilization will be compared across groups. We hypothesize that patients with high depression symptoms will have worse functional outcome, lower quality of life, and higher healthcare utilization. We will also divide patients into groups based on their participation in the Joyable program and compare outcomes (e.g., PHQ-9 score, quality of life, health utilization) between subjects who showed high engagement in the program and those who showed low engagement.

Table 2. Statistical Power for single sample paired t-test

SD of the Difference	Difference in PHQ-9 Pre/Post Treatment				
	1	2	3	4	5
2	61%	99%	100%	100%	100%
3	32%	85%	99%	100%	100%
4	20%	61%	92%	99%	100%
5	15%	43%	77%	95%	99%
6	12%	32%	61%	85%	96%

Data Confidentiality

Internet-based files will only be made available to personnel involved in the study through the use of access privileges and passwords. Paper-based records will be kept in a locked, secure location and only accessible to study personnel. Prior to access to any study-related information, personnel will be required to sign statements agreeing to protect the security and confidentiality of identifiable information. Whenever feasible, identifiers will be removed from study-related information.

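### The Day-90 contact is in-person only, which puts the Day-90 PHQ-9 and the utilization and perceptions items at avoidable risk of possibly selective loss

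*Combined protocol and SAP*

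**What the plan says.** The section headed 90 Day In-person Visit states: "Subjects will be seen by the study team 90 days +/- 14 days after enrollment". At that visit the team takes the NIHSS, PHQ-9, modified Rankin Scale, EQ-5D, healthcare utilization, other mental health treatment, and perceptions of the program. No telephone, video or postal alternative is given.

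The earlier contacts are more flexible. The 72-hour contact may be in person or by telephone. For the 30-day contact the protocol says "Subjects will be contacted by the study team phone or in person at 30 days +/- 7 days after enrollment", and that contact includes the modified Rankin Scale and EQ-5D.

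Table 1 places the study-team PHQ-9 at baseline and Day 90 only. The Analysis Plan compares those two scores and states that "we have >80% power to detect a difference in PHQ-9 of 3 or more points across a range of assumptions". The enrolled number is fixed ("Sample Size: 20 subjects will be enrolled"). No dropout rate, attrition allowance or missing-data rule appears.

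The Analysis Plan also describes a weekly PHQ-9 given through the program and analysed by GEE. Data Confidentiality says the program's PHQ-9 and satisfaction results are sent to the research team.

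**The concern.** PHQ-9 reduction is one of two primary outcomes, and its paired comparison needs a Day-90 score from each subject. As written, a subject who cannot come to the center between Day 76 and Day 104 (90 - 14 and 90 + 14) has no Day-90 record at all. Yet most of that record is questionnaire data that could be taken by telephone.

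Two things are at stake. The first is precision: with 20 subjects, each missed visit removes 1/20 = 5% of the paired data. The second is possible bias: subjects who do not return may differ in mood, disability or engagement from those who do. The planned comparison of high and low engagement needs Day-90 data from low engagers in particular.

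**Working it through.** **Step 1. What a missed visit removes.**

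| Day-90 item | Other post-baseline source | Needs examination? |
|---|---|---|
| PHQ-9 | None from the study team; weekly program score | No |
| EQ-5D | Day 30, telephone allowed | No |
| Modified Rankin Scale | Day 30, telephone allowed | No |
| Antidepressant use | Day 30, telephone allowed | No |
| Other psychotherapy | None | No |
| Utilization survey | None | No |
| Study perceptions items | None; program sends its own satisfaction ratings | No |
| NIHSS | None | Yes |

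The program lasts 8 weeks, or 8 x 7 = 56 days, and the Day-90 window opens at Day 76. Even a subject who finishes on schedule would have a last program score about 76 - 56 = 20 days before the window. A subject who stops using the program has less, and the plan does not name these scores as a Day-90 fallback.

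**Step 2. Reproduce the plan's power.** Inputs: n = 20 (Sample Size); alpha 0.05, sidedness not stated (Analysis Plan); differences of 1 to 5 points and SDs of the difference from 2 to 6 (Table 2). The table is titled "Table 2. Statistical Power for single sample paired t-test", but the formula that fits it is the two-sided normal approximation:

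power = Phi(sqrt(n) x d/SD - 1.96) + Phi(-sqrt(n) x d/SD - 1.96)

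For d = 3, SD = 4, n = 20: sqrt(20) x 0.75 = 3.354; 3.354 - 1.96 = 1.394; Phi(1.394) = 91.8%; the second term is negligible. Table 2 prints 92%. All 25 cells agree, with a largest deviation of 0.47 percentage points. The exact two-sided paired t-test (noncentral t, n - 1 degrees of freedom, noncentrality sqrt(n) x d/SD) matches only 14 of 25 cells within 2 points, and falls up to 4.9 points below the table.

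**Step 3. Power with missing Day-90 scores.** The missing fractions are assumptions. Both methods are shown for d = 3.

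| Assumed missing | n | SD 4, normal | SD 4, exact t | SD 5, normal | SD 5, exact t |
|---|---|---|---|---|---|
| 0% | 20 | 91.8% | 88.9% | 76.5% | 72.1% |
| 10% | 18 | 88.9% | 85.0% | 72.1% | 67.0% |
| 20% | 16 | 85.1% | 80.1% | 67.0% | 61.2% |
| 30% | 14 | 80.1% | 73.7% | 61.2% | 54.7% |

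In Table 2, SD 4 is the largest SD at which a 3-point change exceeds 80% power; SD 5 is already at 77%.

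**Step 4. Possible bias.** The mean change in completers differs from that in all 20 subjects by (missing fraction) x (difference in mean change between completers and non-completers). With 10-30% missing and an assumed 3-point difference, this is 0.1 x 3 = 0.3 to 0.3 x 3 = 0.9 points. With an assumed 5-point difference it is 0.5 to 1.5 points. The formula gives a size for each assumption; the documents do not support any particular value or sign.

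**The case against.** The case for leaving the visit alone has several sound parts.

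- **Eligibility.** The exclusion criteria remove people who cannot comply with follow-up, who need long-term inpatient nursing care, or who are discharged to a skilled nursing facility or hospice. Many foreseeable non-attenders are screened out. This narrows the risk, but does not cover decline or a change of circumstances after enrollment.
- **Travel.** A reader might infer that the protocol itself says its subjects cannot travel to the visit, from the Background sentence "This may be even more difficult for patients with mobility limitations, which are common after stroke". That sentence concerns a course of CBT with 2-3 visits per week for 10-12 weeks, and does not support the inference for a single visit in a 28-day window.
- **Other data.** Activities completed comes from the program and does not depend on the visit. Weekly PHQ-9 scores and program satisfaction ratings also reach the team, and the modified Rankin Scale, EQ-5D and antidepressant use have Day-30 values. The loss is partial.
- **NIHSS.** It is a scheduled Day-90 measure and a legitimate reason to see subjects in person. It is not listed as a primary or secondary outcome, but the exploratory outcome lists are open-ended, so it cannot be called irrelevant to the analysis.
- **Mode.** In a single-arm pre/post comparison, a change of mode enters the change score directly, and with perhaps 2-6 remote scores it cannot be separated out. The EQ-5D visual scale asks for a drawn line, so telephone collection is imperfect, though the 30-day contact already allows it. Some non-attenders may not answer the telephone either, so the fallback would recover only part of the loss.

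These points limit the size of the problem and the benefit of the remedy. They do not explain why the contact carrying the PHQ-9 comparison is the only one without a telephone option.

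**Conclusion.** The point holds as an avoidable design risk; it is not a contradiction in the plan. The Day-90 PHQ-9, the utilization survey and the study perceptions items all hang on one in-person visit with no stated fallback.

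The power loss is moderate. For 3 points at SD 4, going from no missing scores to an assumed 10-30% takes power from 92% to 89-80% on the plan's own approximation, or from 89% to 85-74% by exact t. At SD 5 power is below 80% before any loss. A remote option could at most restore n to 20.

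A reader might infer that data will be lost selectively and that the results will look too favorable. The documents do not support this: they give no attrition figure and no evidence on who would miss the visit. Losing subjects who remain depressed would flatter the change; losing those with high baseline scores, who have most room to improve, could shrink it. Nor is the whole primary outcome set exposed, since activities completed is unaffected.

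**What to change.** Keep the in-person visit as the default and add to the 90 Day In-person Visit section:

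*If a subject cannot attend within 90 +/- 14 days, the study team will collect the PHQ-9, EQ-5D, modified Rankin Scale, utilization, other-treatment and program-assessment items by telephone in the same window. Only the NIHSS will be left missing. The mode of collection will be recorded.*

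Add a mode field to the 90 Day Visit CRF, report the number of Day-90 scores by mode, and repeat the PHQ-9 comparison with in-person scores only as a sensitivity analysis. A staff telephone call is preferable to an unattended link because PHQ-9 item 9 asks about self-harm.

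The cost is a short amendment, one CRF field and some calls by the team that already makes the 30-day contact. The drawback is that a few scores will differ in mode from baseline. The sensitivity analysis can examine this but cannot fully resolve it at this sample size.

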Protocol Title: Internet-based Cognitive Behavioral Therapy to Reduce Depressive Symptoms after Stroke Pilot/Feasibility Study

Short Title: Internet-based CBT for Depression after Stroke Pilot

Investigators:

[name]
[name]
[name]

Brief Description:

Stroke is one of the leading causes of death and disability in the United States, with estimated direct and indirect costs exceeding 70 billion dollars per year. Depression is common after stroke, occurring in approximately 25% of all patients. Depression has been associated with lower quality of life, higher mortality, increased healthcare utilization and higher costs. Cognitive behavioral therapy (CBT) interventions have been shown, in small studies, to both treat and prevent the development of post-stroke depression. CBT based interventions therefore have the potential to improve quality of life and reduce healthcare costs after stroke. Unfortunately, there are significant barriers to the widespread use of CBT in the stroke population, including limited access to licensed providers, high costs of treatment, and limited mobility. Alternative methods for delivering CBT have the potential to improve access and reduce costs and may make widespread dissemination of CBT based treatment possible. We aim to test the feasibility of an internet-based CBT (iCBT) program combined with a telephone/email based coaching service in patients with recent stroke. We will do this by partnering with Joyable. Joyable is an existing, commercially available iCBT program. Joyable's iCBT Program for Depression combines 42 brief online activities with a telephone/email based coaching service, which is designed to motivate and encourage individuals to complete the online modules.

Objectives:

1. Determine the feasibility of internet-based CBT in patients with recent ischemic stroke and depressive symptoms, by quantifying adherence to the program in a pilot population of 20 subjects.
2. Quantify changes in depressive symptoms and quality of life in subjects pre- and post-program participation, to provide preliminary evidence of the efficacy of internet-based CBT to improve outcomes after stroke.

Primary Outcome variables

The primary outcomes will be the number of activities in the iCBT program completed by participants and reduction in depressive symptoms, measured the 9-item Patient Health Questionnaire (PHQ-9).

Secondary Outcome variables

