No clinical information obtained by the research team will be sent to Joyable. De-identified data from Joyable will be sent to the research team, which will include the number of Joyable activities completed by the subject, the number coaching interactions, and results of Joyable administered PHQ-9 and satisfaction assessments. This data will be organized by subject identification number, which can be used to link to the data collected by the research team. The research team will maintain a password protected file on a secured computer at the University of Pennsylvania which will link subject identification number to identifying information for each subject (name, medical record number, date of birth). Access to this file at the University of Pennsylvania will be limited to the PI and the study research coordinator. A Microsoft Excel document will be created which will include subject name, date of birth, and study identifier. This document will be uploaded to Penn+Box. The study team at Joyable will be given access to the file via Penn+Box. They will use this information to link the Joyable data elements described above to each subject. Joyable will then upload a Microsoft Excel file containing this data and subject identifier to the study Penn+Box, where it will be downloaded by the research team.

Patients who enroll in the study will all be participating in Joyable's iCBT Program for Depression. During enrollment in the study, patients will create an account with Joyable. As a part of this process, subjects register with Joyable using the same process as they currently use for their commercially available program. Registration requires the subject to submit the following PHI: name, date of birth, gender, and email address. Access to PHI will be limited to those who need it. This may include the individual coach who is assigned to each subject, coach managers who have access to subject data for the coaches that report to them, Joyable's analytic team which

has access to data for the purpose of aggregating and sharing back results to the research team, and a small number of engineers who can access data in order to troubleshoot bugs in the software. Subject interactions with Joyable will be governed by Joyable's existing Privacy Policy (see <https://joyable.com/privacy>) and terms of use (see <https://joyable.com/terms>).

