 I have some problems washing or dressing myself
 I am unable to wash or dress myself

Usual Activities (e.g. *work, study, housework, family or leisure activities*)

I have no problems with performing my usual activities
 I have some problems with performing my usual activities
 I am unable to perform my usual activities

[figure not shown]
Pain/Discomfort

I have no pain or discomfort
 I have moderate pain or discomfort
 I have extreme pain or discomfort

Anxiety/Depression

I am not anxious or depressed

I am moderately anxious or depressed
 I am extremely anxious or depressed

Now, please write the number you marked on the scale in the box below.

YOUR HEALTH TODAY =

27. Internet/Mobile Device Usage

How do you access the internet? (Select all that apply):

- Computer
- Tablet
- Smart Phone

What is your preferred method of internet access? (Select 1):

- Computer
- Tablet
- Smart Phone

Where do you typically access the internet? (Select all that apply):

- Work
- Home
- Friend/Family member's home
- Public access point (i.e. Library, coffee shop, etc)
- Other: _____

Where is your preferred location to access the internet? (Select 1):

- Work
- Home
- Friend/Family member's home
- Public access point (i.e. Library, coffee shop, etc)
- Other: _____

How often do you typically access the internet? (Select 1):

- More than once a day
- Once a day
- Every couple of days
- Once a week or less

How much time per day do you typically spend on the internet?

- <30 minutes
- 30-59 minutes
- 60-119 minutes
- 120+ minutes

If you have a smartphone or tablet, do you use “Apps?”

- No
- Yes
- Not Applicable - do not own a smartphone or tablet

If you have a smartphone or tablet, do you ever have problems using it (e.g. typing, reading, using the touchscreen)?

- No
- Yes
- Not Applicable - do not own a smartphone or tablet

Have you ever used an “App,” website, or online platform to improve your health before?

- No
- Yes

If yes, how would you rate the experience?

- Not helpful
- Somewhat helpful
- Very helpful
- Not applicable

3. 72-Hour Phone Call

Date: ____ / ____ / ____
day day year

Does the patient have difficulty accessing Joyable? No ⁰ Yes ¹
If yes, please specify what the problem was and how it was addressed:

Name of the person who completed 48 hour follow up:

Signature: _____

Date: ____ / ____ / ____
month day year

4. 30-Day Phone Call

Date: ____ / ____ / ____
day day year

Does the patient have difficulty accessing Joyable? No ⁰ Yes ¹

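### Does the planned time-in-programme metric fail because no data source is named for it?

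*Combined protocol and SAP*

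**What the plan says.** The first paragraph of the Analysis Plan sets two per-subject metrics: time in the programme ("we will calculate the total amount of time spent interacting with the Joyable program") and the count of activities finished. Both are averaged over the study population and read as the dose of CBT delivered. The exploratory analysis of baseline factors in the same paragraph uses the activity count alone.

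Under Data Confidentiality, the protocol describes the de-identified data the vendor will send, "which will include the number of Joyable activities completed by the subject, the number coaching interactions, and results of Joyable administered PHQ-9 and satisfaction assessments". On linkage it adds "They will use this information to link the Joyable data elements described above to each subject", and on transfer "Joyable will then upload a Microsoft Excel file containing this data and subject identifier to the study Penn+Box". The next paragraph of that section, on who may see identifiable data, says the vendor's analytic team "has access to data for the purpose of aggregating and sharing back results to the research team".

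The Primary Outcome variables section states "The primary outcomes will be the number of activities in the iCBT program completed by participants", together with reduction in PHQ-9. Time in the programme is not among the primary or secondary outcomes.

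**The concern.** The Analysis Plan makes a firm commitment to a time metric, and only the vendor's platform could plausibly measure it. Yet the one place that says what the vendor supplies does not mention time, session length or log-ins. Two later sentences in that section refer back to the listed items, which can be read as closing the list. The study's own forms do not fill the gap. The only question about time spent online is item 27 of the baseline form, "How much time per day do you typically spend on the internet", which concerns general internet habits before the programme starts.

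If the file held only the named items, the time average could not be produced, and the site's forms could not recover it later. That matters somewhat in a feasibility study of stroke survivors. Measured time might show that patients with residual disability need longer than the stated 5–10 minutes per activity, or spend time on activities they never finish. A count of completed activities shows neither.

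**Working it through.** No figure in the plan bears on this point, so the check compares the sections and then traces what depends on time.

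**1. Where each platform-generated item appears.** The vendor description names four elements, Table 1 has ten rows, and the Appendix has five forms.

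| Item | Role in the plan | Vendor description | Table 1 | Appendix forms |
|---|---|---|---|---|
| Activities completed | Primary outcome | Named | Absent | Absent |
| Number of coaching interactions | Secondary outcome | Named | Absent | Absent |
| PHQ-9 given weekly by the platform | GEE analysis | Named | Absent | Absent |
| Time in the programme | Descriptive dose metric | Not named | Absent | Absent |

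The PHQ-9 row in Table 1 is the study team's own assessment at baseline and day 90, not the weekly platform score. The 90-day form asks how satisfied the subject was with the coach, not how many contacts took place.

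Table 1 and the forms therefore give the same answer, absent, for all four items, including a primary outcome whose source is not in doubt. They record what the study team collects at its own four contacts and cannot show whether a platform item is available. Only the vendor description distinguishes time from the other three.

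**2. How much weight the vendor description carries.** It stands in a section about identifiers, linkage and access, and it is introduced by wording that need not be exhaustive. It is also coarser than a data specification. It promises PHQ-9 results without mentioning the assessment week, although the GEE model needs week as its independent variable. A list that leaves out a field the planned model cannot do without is evidently a summary. The back-references in the linkage and transfer sentences point to this same summary and do not independently limit it. The remark about the vendor's team sharing results back is general, and neither includes nor excludes time.

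**3. What depends on time.**

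- Primary adherence outcome: activity count; does not use time.
- Primary PHQ-9 outcome, the GEE model and Table 2: PHQ-9 scores; do not use time.
- Secondary outcomes (completion, coaching contacts, EQ-5D, healthcare utilization, satisfaction): none is defined by time.
- Exploratory analysis of baseline factors: activity count.
- Exploratory high/low engagement comparison: no metric named, so its dependence on time cannot be determined from the text. The activity count would serve.
- Average dose: time is one of two metrics, so 1 of 2 is exposed.

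**4. Whether activity counts could stand in for time.** The protocol gives 42 activities, most taking about 5–10 minutes. A full completer would have a nominal 42 × 5 = 210 to 42 × 10 = 420 minutes, that is 3.5 to 7 hours. This only rescales the activity count. It ignores unfinished sessions and coaching, and the plan does not propose it. It is not a substitute for logged time, but it gives the scale of the quantity.

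**The case for a change.** The best argument for a change is that the mismatch is real and cheap to remove. One section promises a calculation and another describes the incoming data without the needed item, and nothing else in the documents supplies it. The sentences on linkage and upload refer to the items already described, so a reader who took the section literally would build a file without time. Adherence is the first objective of the pilot, time would add something that counts do not, and a single question to the vendor before enrolment would settle it.

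Part of this stands. Time is not named anywhere as a supplied item, and literal use of the vendor description would omit it. What does not stand is the step from not named to not available. The documents do not say what the platform logs or what the data agreement covers. Asking the vendor is ordinary work in setting up a data transfer, and it needs no different rule in the plan. Either answer leaves every outcome and conclusion as it was. Time is reported if it is logged, with a note on how idle time and coaching contact are treated. If it is not logged, the activity count alone describes dose.

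**Conclusion.** No change to the plan is needed. There is a minor mismatch between the Analysis Plan and the Data Confidentiality section, amounting to missing detail: no stated rule produces a wrong result. The loss of the time metric is a conjecture based on the silence of one summary list. If it occurred, it would remove one of two descriptive averages in 20 subjects and leave the primary and secondary outcomes, the GEE analysis, the baseline-factor analysis and the power table untouched.

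This rests on two assumptions. The first is that the vendor description is a summary, not a closed specification; its missing assessment week supports that reading. The second is that the engagement comparison is not meant to depend on time alone. The text leaves that open, but the comparison is exploratory and the activity count is available for it. If the second assumption failed, the effect would still be confined to that one exploratory comparison.
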